## **Sample Size Estimation and Statistical Approach**

Sample size estimates are based on feasibility of recruitment in a 1 year study period and anticipated attrition rates, based on our experience recruiting similar patient populations. Estimates derived from the current pilot trial in the form of posterior distribution will form the basis for simulations in planning the subsequent, larger, confirmatory trial.

Descriptive statistics will characterize the proportion of randomized patients completing assessments at baseline, 7 days (intervention), 1 month (intervention), 3 months (intervention), 5-months (intervention) and 6 months (all). Tabulation of obstacles to the intervention and completion of the outcome assessments will permit appropriate revision of the intervention for the subsequent, larger confirmatory trial. Descriptive statistics will characterize scores on the Telemedicine Satisfaction Questionnaire. Inspection of patterns of patient responses to specific

IRB NUMBER: HSC-MS-18-0925

items will permit modification of the telemedicine approach for the subsequent, larger, confirmatory trial. Generalized linear modeling will evaluate the primary clinical outcome difference in ambulatory daytime systolic BP between the two groups 6 months post-discharge as a function of treatment, race, the interaction of treatment and race, the interaction of insurance status and race. Secondary analyses will evaluate nighttime systolic, and daytime and nighttime diastolic ambulatory BP, BMI, recurrent vascular event rate, acute healthcare utilization rate, self-efficacy, medication adherence, and caregiver burden.

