Hypertension is the most important risk factor for ischemic stroke and hemorrhagic stroke. Small reductions in systolic BP after stroke (5 mmHg) are associated with greater than 20% reduction in recurrent stroke risk. However, available data suggests that hypertension remains poorly controlled after the incident stroke. A report from the Reasons for Geographic and Racial Differences in Stroke (**REGARDS**) observational study revealed that risk factor awareness and control were poor in participants who self-reported a history of stroke. Only 66.7% of stroke survivors had controlled BP, and African American stroke survivors were more likely to have undiagnosed hypertension and uncontrolled hypertension (among those treated) than White stroke survivors. Baseline visit data from the Secondary Prevention of Small Subcortical Strokes (**SPS3**) trial support REGARDS data. Among US participants, 44% of ischemic stroke survivors had controlled BP three months after stroke and African Americans were more likely to have uncontrolled BP. Investigators from The Differences in the Imaging of Primary Hemorrhage based on Ethnicity or Race (**DECIPHER**) project reported poor BP control 30 days and 1 year after hemorrhagic stroke. In this study, BP was controlled (less than 140/90) for 47.2% of participants at 30 days and for 41.7% one year after stroke, and BP control was poor in African Americans.

Factors associated with BP control in African Americans have been studied extensively. These include social and economic factors, condition and therapy-related factors, health care system and clinician factors, patient-related factors, and patient-physician relationship factors. Uncontrolled BP may be specifically related to medication cost, access to healthcare, access to providers, medication complexity, patient beliefs and perceptions, patient educational achievement and socioeconomic status, patient response to and side effects of medications, sodium intake, patient depression and demoralization, perceived racism and discrimination, social networks and support, physician prescribing practices, physician communication and empathy, neighborhood segregation, and others.

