We will implement a pilot trial of a telehealth intervention for BP control at the Memorial Hermann Hospital-TMC campus focusing on patients at highest risk for uncontrolled blood pressure. The intervention will address general and stroke-related factors associated with racial disparities in BP control. We will assess feasibility of implementation of the trial and will use the measures and outcomes assessed in the pilot to examine knowledge gaps.

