### Aim 2 will shift from the planning portion of the study to the pilot trial, which will simulate a larger trial and allow evaluation of intervention components and outcome measures and estimation of effect sizes and attrition rates.

- Aim 2a: To examine the suitability of key study components and outcome measures intended for a future larger trial, we will randomize 50 patients to the intervention and 50 patients to usual care. We will determine the proportion of randomized patients who complete the intervention visits, the proportion of patients (by group) who complete the outcome assessments, and barriers to intervention and 6-month outcome assessment completion.
- Aim 2b: To examine the suitability and ease of use of the telehealth tool and effectiveness of components of the intervention, we will develop a CRF to capture patient feedback to be integrated into the design of the future, larger trial.
- Aim 2c: To estimate key parameters needed to adequately power a larger randomized trial, we will calculate the effect of the intervention on the ambulatory systolic blood pressure at 6 months relative to usual care; the probability using Bayesian methods that this effect size exists; the enrollment rate; and the attrition rate.

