## Screening and Randomization

Sequential eligible patients will be approached prior to discharge to assess their interest in participating in the trial. Informed consent will be obtained from patients. Caregivers will provide consent for patients with aphasia who are otherwise eligible. Baseline assessments of socioeconomic status (education and income), medication adherence, medication adherence self-efficacy, cognition, and social support will be completed prior to randomization. We will use an internet-based system to randomize patients (1:1) to intervention versus usual care using a block design with permuted blocks of 2 to 4. The randomization allocation sequence will be developed by a statistician not involved in enrollment procedures. We will stratify based on insurance status (insured vs uninsured) and race (African American vs other) to assure that groups are balanced with respect to baseline risk. Consort criteria for the design of parallel group randomized trials will be followed.

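### Does an Aim 2c probability with no threshold, and an overall treatment contrast that is not named, weaken what the pilot hands to the larger trial?

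*Combined protocol and SAP*

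**What the plan says.** Under Specific Aims, Aim 2c lists what the pilot must supply for powering a larger trial. Four quantities are named: an effect ("we will calculate the effect of the intervention on the ambulatory systolic blood pressure at 6 months relative to usual care"), a Bayesian quantity ("the probability using Bayesian methods that this effect size exists"), the enrollment rate and the attrition rate. No threshold, direction or prior is attached to the second.

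The section Sample Size Estimation and Statistical Approach gives a generalized linear model for the difference in daytime systolic "BP between the two groups 6 months post-discharge as a function of treatment, race, the interaction of treatment and race", with a further insurance-by-race term. It gives no coding, reference group or weights for averaging over race. It also says what is carried forward: "Estimates derived from the current pilot trial in the form of posterior distribution will form the basis for simulations" used to plan the confirmatory trial. The sample size is set by feasibility.

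Race matters by design. Under Screening and Randomization the plan states "We will stratify based on insurance status (insured vs uninsured) and race (African American vs other"), and the background section says "The intervention will address general and stroke-related factors associated with racial disparities in BP control".

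**The concern.** Two things look wrong on a first reading.

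First, the Bayesian probability refers back to the effect just estimated. Under a continuous prior, the probability that the effect equals one exact value is 0. The probability that it is at least the estimate is one half under a flat prior, and under a prior centred on zero it falls as the observed benefit grows. On those readings a null pilot scores as well as a promising one, or better.

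Second, Aim 2c wants one effect, but the model includes treatment by race. With 0/1 coding, the coefficient labelled treatment is the effect in the reference race group only. If that number were taken as the overall effect, the larger trial could be planned on the wrong quantity and with a needlessly wide interval.

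**Working it through.** The plan has no figure to reproduce here: 50 + 50 = 100 is a feasibility number with no power calculation behind it. The SD, completer numbers, race shares, effects by race and priors below are assumptions, not values from the documents.

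**The probability.** Take 80 completers and SD 15 mmHg. The standard error of the difference is 15 × √(4/80) = 3.35 mmHg. With a normal prior of mean 0 and SD t, the weight is w = t²/(t² + 3.35²), the posterior mean is w × estimate, and the posterior SD is √w × 3.35. For t = 10, w = 100/111.25 = 0.899 and the posterior SD is 3.18. At an estimate of 8 the posterior mean is 7.19.

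| Estimated reduction (mmHg) | 0 | 2 | 5 | 8 |
|---|---|---|---|---|
| P(at least the estimate), flat prior | 0.50 | 0.50 | 0.50 | 0.50 |
| P(at least the estimate), t = 10 | 0.50 | 0.47 | 0.44 | 0.40 |
| P(at least the estimate), t = 5 | 0.50 | 0.41 | 0.29 | 0.19 |
| P(any reduction), t = 10 | 0.50 | 0.71 | 0.92 | 0.99 |

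The first three rows confirm that the literal reading tells the investigator nothing useful. The last row shows that the probability that a benefit exists does separate weak pilots from strong ones.

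The unstated prior has little influence on that last quantity. For t = 5, 10 and 20 and a flat prior in turn, P(any reduction) is:

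- estimate 2: 0.690, 0.714, 0.722, 0.725
- estimate 5: 0.892, 0.921, 0.929, 0.932
- estimate 8: 0.976, 0.988, 0.991, 0.991

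The widest spread is 0.725 − 0.690 = 0.035 at an estimate of 2, and 0.932 − 0.892 = 0.040 at an estimate of 5.

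**The contrast.** Take 100 patients, 40% African American, SD 15 mmHg, and true reductions of 8 mmHg (African American) and 2 mmHg (other), chosen to make the issue visible. The insurance-by-race term is left out; it does not involve treatment and so does not change what the treatment contrast means.

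| Quantity | Effect (mmHg) | Standard error |
|---|---|---|
| Coefficient, other as reference | 2.0 | 15 × √(4/60) = 3.87 |
| Coefficient, African American as reference | 8.0 | 15 × √(4/40) = 4.74 |
| Equal weights | 5.0 | 3.06 |
| Weights from the race mix | 4.4 | √(0.4² × 22.5 + 0.6² × 15) = 3.00 |

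These are different summaries of one fitted model. The overall effect comes from either coding: 2.0 + 0.4 × 6 = 4.4, and 8.0 − 0.6 × 6 = 4.4. The larger standard errors in the first two rows belong to a different question, the effect in one race group, and are not a loss built into the plan. If the effect does not differ by race, all four rows have the same expected value.

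**The use made of them.** The simulations take a posterior distribution as input. Any tail probability can be read from it, and the joint posterior of the coefficients with an assumed race mix gives the overall effect for any future population.

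**The case for a change.** The strongest case for a change is that Aim 2c exists to power the next trial, and an unnamed contrast could move that calculation a great deal. In the illustration above, at SD 15, two-sided 5% and 80% power, reductions of 2.0, 8.0, 5.0 and 4.4 mmHg imply 883, 56, 142 and 183 patients per arm. The plan itself treats a difference by race as plausible, naming the contrast and prior costs a sentence, and settling them early prevents a choice made after the results are seen.

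The arithmetic stands, and so does the observation that the text never says the probability means any reduction. But the extremes of 883 and 56 arise only if an analyst presents a single-race coefficient as the overall effect. Nothing in the plan says so, and its wording points the other way: it speaks of a difference between the two groups and of an effect relative to usual care.

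A named clinical threshold would add a quantity that the plan does not promise. The only candidate is background: "Small reductions in systolic BP after stroke (5 mmHg) are associated with greater than 20% reduction in recurrent stroke risk" is not tied to daytime ambulatory pressure or to Aim 2c. That quantity would also depend more on the prior: at an estimate of 8 mmHg with 80 completers, the probability of a reduction of at least 5 is 0.57, 0.75 and 0.80 for prior SDs of 5, 10 and 20.

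Replacing the planned model with main effects only would bring no clear gain. With balanced completers it gives the same overall estimate as the race-standardised contrast. With uneven dropout the two differ by an SD of roughly 0.2 to 0.5 mmHg, depending on how dropout is modelled, against a standard error of about 3.4. It would also drop the plan's insurance-by-race term and move treatment by race out of the primary model, a debatable choice in a trial about racial disparities.

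**Conclusion.** No change is needed. Aim 2c's probability is loosely worded and the averaging over race is unstated, but both are details that a competent Bayesian analyst would fill in sensibly: the probability of any reduction, and an overall contrast from the planned model with treatment by race reported beside it. Under the assumptions used (80 completers, SD 15 mmHg, zero-centred normal priors with SD 5 to 20, or a flat prior), that probability is informative and moves by no more than about 0.04 with the choice of prior at estimates of 2, 5 and 8 mmHg. The overall effect is recoverable from the same fit whatever the coding. No stated figure, stopping rule or go/no-go rule depends on either point, the sample size of 100 is unaffected, and the retained posterior already supports the planned simulations. The conclusion would be different only if a later report gave a single-race coefficient as the overall effect, or gave the probability of exceeding the estimate as evidence of benefit. The plan commits to neither.

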## Specific Aims

### Aim 1 will focus on the identification of hospitalized ischemic and hemorrhagic stroke patients at risk for uncontrolled BP after hospital discharge.

- We will develop a checklist to be completed by the discharge nurse navigator or social worker for early identification of stroke inpatients at risk for uncontrolled BP. The checklist will include existing information from the patient medical record (race and insurance) and clinical information including stroke type and etiology in order to document the presence of known risk factors for uncontrolled BP. Key known risk factors include uninsured status, Medicaid payer status, hypertensive intracerebral hemorrhage, small vessel ischemic stroke, and patients on  $\geq 2$  hypertensive medications. The checklist will be used to determine which patients should be screened for study eligibility.

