## Intervention

Components of the telehealth intervention will target behaviors associated with racial disparities (African American focused) in BP control. At the time of discharge, intervention patients will receive a package containing an iPad (with a data plan) and a blue tooth enabled blood pressure monitor that allows automatic transmission of encrypted BP data to the study team (QardioARM). Patients will be allowed to use their own smart device if it is compatible with the BP device). Patients and/or caregivers will be instructed in use of equipment and the first video telehealth visit will be arranged. They will complete questionnaires including a depression screen, a dietary assessment, a cognitive screen, and a sleep apnea screen prior to discharge. Patients will receive a phone call at 72 hours by the discharge nurse navigator or social worker (standard of care) to assure that they have received their medications and follow-up appointments. The first telehealth visit will occur 7 days after discharge. A stroke prevention-trained nurse practitioner (**NP**) or **MD**, social worker (**SW**), and pharmacist will attend this video telehealth visit. The NP will review the participant's hospital records and depression, dietary, and sleep apnea screens, will reinforce the care plan based on patient-specific needs. The NP or MD will counsel patients on salt reduction, the Mediterranean diet, and the importance of diet and exercise for stroke prevention. The NP (or MD) and pharmacist will review the BP data to determine the need for medication adjustment. The pharmacist will discuss side effects and

interactions. Treatment of hypertension and selection of BP lowering medications will be in accordance with latest published guidelines for BP management. The SW will assess the need for medication assistance and other resources. The care plan will be shared with primary care providers (PCP) and patients will be referred to a PCP if they do not have one. The SW will assist uninsured patients in applying for Texas County Indigent Care programs.

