#### **Uninsured Patients (5/8/2019):**

An Internal Medicine Consultant will be utilized as an advisor when complex medical non-neurologic issues arise for patients who do not yet have a primary care provider. The consultant will join the telehealth visits as appropriate to provide recommendations for management of complex medical issues that can be managed in the ambulatory setting.

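### The primary model lists insurance × race without an insurance main effect, so the fitted model depends on coding and the treatment estimate can shift if attrition is uneven

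*Combined protocol and SAP*

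**What the plan says.** Under Sample Size Estimation and Statistical Approach, a generalized linear model compares 6-month daytime ambulatory systolic BP between arms "as a function of treatment, race, the interaction of treatment and race, the interaction of insurance status and race". Race has its own term; insurance does not. No section gives the variable coding, the software, or the contrast that will be reported as the treatment effect.

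Elsewhere the plan treats insurance as prognostic. Screening and Randomization says "We will stratify based on insurance status (insured vs uninsured) and race (African American vs other) to assure that groups are balanced". Aim 1 says "Key known risk factors include uninsured status, Medicaid payer status". Insurance status is among the baseline variables collected.

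The result has a stated use. Under Aim 2c, "we will calculate the effect of the intervention on the ambulatory systolic blood pressure at 6 months relative to usual care". The statistical section adds: "Estimates derived from the current pilot trial in the form of posterior distribution will form the basis for simulations".

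**The concern.** An interaction entered without one of its main effects makes the fit depend on arbitrary coding. With 0/1 products, the insurance effect is set to zero in whichever race is coded 0. With ±1 coding, it is forced to be equal and opposite in the two races. With factor coding, the term may be expanded as insurance nested within race, which is the full model. Two analysts following the same sentence could therefore fit different models.

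Stratified blocks balance insurance across arms at randomisation, but the analysis uses patients with a 6-month BP. Attrition is expected: the sample size rests on "feasibility of recruitment in a 1 year study period and anticipated attrition rates". Some help for uninsured patients is described only for the intervention arm. "The SW will assist uninsured patients in applying for Texas County Indigent Care programs", and for patients without a primary care provider, "The consultant will join the telehealth visits as appropriate to provide recommendations for management of complex medical issues". Retention of uninsured patients could therefore differ by arm, in a direction the documents do not give. If it does, a model that ignores insurance in one race carries that imbalance into the treatment estimate, the treatment × race term and the posterior passed to the next trial's simulations.

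**Working it through.** The plan has no figure to reproduce: it gives no SD, effect size or attrition rate.

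**From the documents:** 100 patients, 1:1 allocation, strata of insurance (insured, uninsured) and race (African American, other).

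**Assumed:** SD 15 mmHg; 50% African American; 40% uninsured, so each arm has 15 insured and 10 uninsured per race; uninsured BP higher by d = 8 mmHg; treatment effects of -6 (African American) and -1 (other). The overall effect is the race-specific effects averaged over the patients analysed.

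**Balanced arms.** The overall effect is 0.5 × (-6) + 0.5 × (-1) = -3.50 with or without the insurance term. Only the model-based SE changes. As listed it is sqrt((225 + 0.5 × 0.4 × 0.6 × 64) × 4/n), which is 3.05 at n = 100 and 3.33 at n = 84. With insurance added it is sqrt(225 × 4/n), which is 3.00 and 3.27.

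**Four uninsured 'other' controls lost (n = 96).** Among 'other' patients, 10/25 are now uninsured in the intervention arm and 6/21 in the control arm.

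- Insurance added: (46 × (-1) + 50 × (-6))/96 = -3.60.
- As listed, 0/1 products, 'other' as reference: the effect in 'other' is -1 + 8 × (10/25 - 6/21) = -0.09, so the overall effect is (46 × (-0.09) + 50 × (-6))/96 = -3.17.
- Shift: (46/96) × 8 × (10/25 - 6/21) = 0.44 mmHg, or 0.44/3.1 ≈ 0.14 SE.
- Treatment × race: -5.91 as listed, -5.00 with insurance added.
- Flat-prior probability that the difference is below zero: Φ(3.17/3.12) = 0.85 against Φ(3.60/3.08) = 0.88.
- As listed, African American as reference: -3.60.
- The same listed terms in one formula interface: factors give 6 columns and -3.60; 0/1 numeric variables give 5 columns and -3.17.

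**Other patterns (0/1 products, 'other' as reference unless stated)**

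| Pattern | As listed | Insurance added |
|---|---|---|
| Four uninsured controls lost in each race (either reference) | -3.04 | -3.50 |
| Two uninsured controls lost in each race | -3.29 | -3.50 |
| Four 'other' lost, uninsured BP lower by 8 mmHg | -4.04 | -3.60 |

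For 20-60% uninsured and d of 4-12 mmHg, losing four uninsured 'other' controls shifts the effect by 0.15 to 0.88 mmHg; losing two shifts it by 0.07 to 0.41.

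**Random attrition.** With 16% loss in every cell, the mean shift over 4,000 replicates is 0 (95% range -0.49 to +0.50 mmHg). With 30% or 40% loss among uninsured controls and 16% elsewhere, the mean shift is about +0.2 or +0.3.

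**Different assumptions.** Take a true effect of -5 in both races, d = 8, 40% of uninsured controls lost and about 7-10% lost elsewhere (n = 86). The listed terms give -4.27 in the reference race, since 8 × (9/23 - 6/20) = 0.73, and -5.00 in the other race. The average is -4.63 under either 0/1 reference. With insurance added, both races return -5.00. The simulated SE is about 3.3 mmHg.

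**The case against.** The strongest reply is that a prose sentence is not a model statement. Race and insurance are two-level categories; entered as factors, the listed terms can give the full model, and the list may be shorthand for a hierarchical one. That is fair, and the documents do not show that the wrong model would be fitted. But the sentence writes out the race main effect beside its interaction and does not do so for insurance, and nothing in the plan settles which reading applies.

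Second, several conditions must coincide: coding that does not recover the full model, a real insurance effect, and loss uneven by arm and insurance where that effect is left unfitted. The central example puts all its losses in one cell (four of ten), and the top of the range, 0.88, needs four of five lost. This stands. The same four losses split evenly between the races shift the effect by only 0.21 mmHg.

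Third, usual-care patients also have retention support: coordinator contacts at 30, 90 and 150 days and an offered clinic visit. Both arms may have a home outcome visit and are paid for the final assessment. These measures may lessen differential loss but do not rule it out.

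Finally, a shift of a few tenths of a mmHg is minor beside an SE of about 3 in a pilot with no decision threshold. That is also true, and it limits how much weight the point should carry.

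**Conclusion.** The concern holds. The listed terms omit the main effect of a stratification factor that the plan regards as prognostic, and they fit five or six parameters depending on coding. The treatment estimate is unaffected while the arms stay balanced on insurance within race. In the central uneven-loss case it moves by 0.44 mmHg (about 0.14 SE) and the treatment × race term by 0.91. Every magnitude rests on assumed BP differences, stratum shares and attrition, and the sign of the shift is unknown. It should be fixed because the remedy costs almost nothing and leaves one defined primary model; the pilot's conclusions are not in danger.

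**What to change.** Before analysis, state the primary model as treatment + race + insurance + race × insurance + treatment × race, with race and insurance at their randomisation levels. All four strata are then fitted whatever the coding or software. In the example this returns -3.60 even with a true race × insurance interaction of -6 mmHg. The planned treatment × race term stays.

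As an accompanying clarification, not a correction of an error, say that the Aim 2c estimate is the overall effect averaged over the observed race distribution. With 'other' coded 0 this is b1 + p × b3, where b1 is the treatment coefficient, b3 the treatment × race coefficient and p the African American share. Report race-specific effects with intervals as descriptive.

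The cost is one model term, one degree of freedom and one sentence, with no new data or patients. The added term corrects imbalance on insurance only and does not deal with other causes of missing 6-month BP.

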## Study Procedures:

## Eligibility Criteria

Ischemic and hemorrhagic stroke patients (N=100) identified as potentially eligible by the checklist (at least one of the following high risk criteria: uninsured, Medicaid payer status, small vessel ischemic stroke, hypertensive ICH, planning on discharging on  $\geq 2$  hypertension medications) will be eligible if they also meet the following inclusion criteria: age  $\geq 18$ ; presence of hypertension (by clinical history or hospital BP  $\geq 130/80$  mmHg on two occasions); plan to discharge home after stroke; ability to provide consent (patient or caregiver); ability to communicate in English. Exclusion criteria will include modified Rankin scale  $> 4$  at the time of enrollment (severe disability), life expectancy  $< 1$  year or terminal illness, eGFR  $< 30$  at time of discharge, pregnancy, symptomatic flow limiting carotid stenosis without plan for intervention; urine toxicology positive for cocaine or methamphetamine or history of use; long-term BP goal  $\geq 130/80$  mmHg according to clinical team; and inability to comply with study procedures \* (severe expressive language impairment, deafness, blindness, or other physical; cognitive; or social issues limiting ability to adhere to procedures).

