## **Variables and Outcome Assessment**

Baseline demographic and clinical characteristics will be abstracted from inpatient charts, supplemented by a study CRF collected prior to randomization. Demographic variables will include age, sex, self-reported race, self-reported ethnicity, level of education, household income, insurance status, and marital status. Clinical variables will include stroke subtype, stroke etiology, prior stroke or TIA, treatment with IV tPA, endovascular therapy, admission National Institutes of Health Stroke Score, pre-stroke modified Rankin scale, presence of stroke risk factors (hypertension, diabetes mellitus, tobacco use, hyperlipidemia, obstructive sleep apnea, atrial fibrillation, coronary artery disease, systolic heart failure, substance abuse) other medical co-morbidities (obesity, chronic kidney disease), Barthel Index at baseline, Body Mass Index (BMI) at discharge, and the number of BP medications at discharge. Psychological, cognitive, and behavioral variables will include depression (Patient Health Questionnaire-9); anxiety (Generalized Anxiety Disorder-7); cognitive impairment (Montreal Cognitive Assessment), self-efficacy (Medication Adherence Self-Efficacy Scale - MASES); medication adherence (Morisky Medication Adherence Scale - MMAS); and social support (Stroke Social Network Scale).

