## **Primary Clinical Outcomes**

The primary clinical outcome will be the daytime ambulatory systolic blood pressure at 6 months. Secondary clinical outcomes will include the following: daytime ambulatory diastolic blood pressure, nighttime ambulatory systolic and diastolic blood pressure; BMI at 6 months; recurrent vascular event rate (stroke, myocardial infarction, acute cardiac death); and acute healthcare utilization rate (hospital readmission and acute care visits to emergency room and/or urgent care). The 6- month behavioral outcomes will include change in self-efficacy for taking medication as prescribed, medication adherence, and caregiver burden. Patient satisfaction will be assessed using scores obtained from the Patient Telemedicine Satisfaction Survey.

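### The primary model for 6-month daytime systolic BP has no baseline BP term, and no measured BP is on the baseline list, so precision available at almost no cost is given up

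*Combined protocol and SAP*

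**What the plan says.** The endpoint is a follow-up value, not a change from baseline: "The primary clinical outcome will be the daytime ambulatory systolic blood pressure at 6 months" (Primary Clinical Outcomes). Under Sample Size Estimation and Statistical Approach, it is to be analysed by generalized linear modeling "as a function of treatment, race, the interaction of treatment and race, the interaction of insurance status and race". No BP covariate is named there.

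The baseline data do not supply one either:

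- Screening and Randomization: "Baseline assessments of socioeconomic status (education and income), medication adherence, medication adherence self-efficacy, cognition, and social support will be completed prior to randomization". BP is not among these.
- Variables and Outcome Assessment: "Baseline demographic and clinical characteristics will be abstracted from inpatient charts, supplemented by a study CRF collected prior to randomization". The list that follows includes hypertension as a risk factor, and "Body Mass Index (BMI) at discharge, and the number of BP medications at discharge", but no systolic or diastolic value.
- Eligibility Criteria: the hypertension criterion is "presence of hypertension (by clinical history or hospital BP" at or above a threshold on two occasions. History alone is enough, so a reading need not be recorded for every patient.
- Outcome Assessments: ambulatory monitoring is described only for the final visit.
- Intervention: home telemonitoring starts after discharge and only in the intervention arm, so it cannot serve as a baseline.

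On how the estimate will be used, Aim 2c says "we will calculate the effect of the intervention on the ambulatory systolic blood pressure at 6 months relative to usual care", in order to power a larger trial. The statistical section adds: "Estimates derived from the current pilot trial in the form of posterior distribution will form the basis for simulations in planning the subsequent" larger trial.

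**The concern.** When a continuous outcome is measured at follow-up, its pre-randomization value is usually the first candidate covariate. Leaving it out does not bias a randomized comparison, but variance that it could have explained stays in the residual. Here the sample size is fixed by feasibility, so covariate adjustment is one of the few ways to sharpen the estimate without more patients. Randomization is stratified by insurance and race, not by BP, so chance imbalance in starting BP is not controlled by design either.

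Two things are at stake. First, a wider posterior for the treatment effect carries straight into the confirmatory-trial simulations. Second, with no baseline BP recorded, the pilot cannot estimate the baseline-to-6-month correlation or the adjusted residual variance. Those simulations would need both if the larger trial adjusts for baseline BP.

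The nighttime and diastolic ambulatory outcomes have the same gap. For BMI the baseline value is collected at discharge, but no adjustment for it is stated.

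**Working it through.** **No stated figure to reproduce.** The plan randomizes 100 patients, 50 per arm, on grounds of feasibility and expected attrition. It gives no SD, effect size, alpha, power, attrition rate or correlation. Every r and SD below is therefore an assumption, shown over a range.

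**Variance factor.** With r the correlation between baseline and 6-month systolic BP, adjustment multiplies the variance of the treatment effect by 1 − r². The equivalent sample size is 100/(1 − r²). Estimating one extra slope costs a factor of about 1 + 1/(N − 4) = 1 + 1/96 = 1.010. The half-width is 1.96 × SD × √(2/50) × √(1 − r²). Unadjusted, this is 1.96 × 3.00 = 5.88 mmHg at SD 15 and 1.96 × 3.60 = 7.06 mmHg at SD 18.

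| Assumed r | 1 − r² | Equivalent N | Net of extra parameter | Half-width, SD 15 | Half-width, SD 18 |
|---|---|---|---|---|---|
| 0 | 1.00 | 100 | 99 | 5.88 | 7.06 |
| 0.1 | 0.99 | 101 | 100 | 5.85 | 7.02 |
| 0.2 | 0.96 | 104 | 103 | 5.76 | 6.91 |
| 0.3 | 0.91 | 110 | 109 | 5.61 | 6.73 |
| 0.4 | 0.84 | 119 | 118 | 5.39 | 6.47 |
| 0.5 | 0.75 | 133 | 132 | 5.09 | 6.11 |

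The half-widths leave out the roughly 0.5% widening from the extra parameter (√1.010 ≈ 1.005).

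**Check by simulation.** In 20,000 simulated trials with 50 per arm, comparing a treatment-only model with and without the covariate, the ratio of adjusted to unadjusted variance was 1.010, 0.973 and 0.762 at r = 0, 0.2 and 0.5. The formula (1 − r²) × 1.010 gives 1.010, 0.970 and 0.758. Both estimators centred on the true value of zero, which confirms that there is no bias.

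**With attrition.** If 20% are lost (assumed; 40 per arm) and SD is 15, the unadjusted half-width is 1.96 × 15 × √(2/40) = 6.57 mmHg. It falls to 6.44, 6.27 and 5.69 at r = 0.2, 0.3 and 0.5. The ratios do not change.

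**The same loss seen as imbalance (not an additional loss).** With a baseline SD of 18, the standard error of the between-arm difference in starting BP is 18 × √(2/50) = 3.6 mmHg. If the outcome SD is also 18, the regression slope equals r. A one-standard-error imbalance then shifts the unadjusted estimate by 0.2 × 3.6 = 0.7 to 0.5 × 3.6 = 1.8 mmHg. If the outcome SD is 15, the slope is r × 15/18 and the shift is 0.6 to 1.5 mmHg.

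**Consequence for planning.** For a next trial with an assumed SD of 15 mmHg, difference of 5 mmHg, two-sided 0.05 and 80% power, about 142 patients per arm are needed unadjusted, 129 if r = 0.3 and 106 if r = 0.5. The value of r therefore matters to the design of that trial, and the pilot as planned cannot estimate it.

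**The case against.** The strongest reply is that the loss is conditional. The only BP likely to exist before randomization is an inpatient reading after acute stroke, and the endpoint is an ambulatory reading six months later. Medication adjustment toward a BP target in the intervention arm could weaken the link further. At r = 0.1 the gain only pays for the extra parameter. At r = 0.2 and SD 15 the half-width moves by 5.88 − 5.76 = 0.12 mmHg, which would not alter any plan. This stands: the gain may be small, and the upper end of the range should not be assumed.

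Three technical points also stand as refinements. The relevant r is the partial correlation given race and insurance, which the model already contains and which the background links to BP control. The half-widths apply to an overall treatment contrast, not to a race-specific coefficient from the interaction model. They also assume that all 50 per arm complete. None of these reverses the direction of the result.

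It can be said too that the pilot would estimate r poorly: with 100 completers, an observed 0.3 has a 95% interval of about 0.11 to 0.47. That is so, but the interval can be carried into the simulations, whereas the plan as written supplies no estimate at all. Evidence that r is small would itself be useful for planning.

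Finally, this is a feasibility pilot, the unadjusted contrast is valid, and the charts will hold BP values even though the list does not ask for them. The last point shows that the gap is easy to close, not that it is closed. Effect estimation is a stated aim, so pilot status does not dispose of the matter.

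**Conclusion.** The concern holds. The primary model has no baseline BP term, no measured BP is on the list of data to be collected, and no other section supplies either. There is no bias; the consequence is a loss of precision whose size is unknown because the documents give no correlation.

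At assumed r of 0.2 to 0.5 the plan forgoes a 4% to 25% reduction in variance, the equivalent of 3 to 32 extra patients net of the added parameter. Near r = 0.1 the trade is neutral, and at r = 0 adjustment costs about 1%. In-hospital BP is a proxy for a baseline ambulatory reading, so adjustment removes only the part of the variation that the proxy predicts. The omission is certain from the text; how much it costs is not. The change should be made because the possible gain clearly exceeds the possible cost, and because the confirmatory-trial simulations would otherwise have no estimate of r.

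**What to change.** 1. Add to the baseline list one defined pre-randomization hospital systolic and diastolic BP, abstracted from the inpatient chart for every patient in both arms. One workable definition is the mean of readings in the 24 hours before randomization.
2. Prespecify that systolic value as a covariate in the primary model and the nighttime systolic model, and the diastolic value in the daytime and nighttime diastolic models.
3. Adjust 6-month BMI for the discharge BMI already collected.
4. Report the observed correlation between baseline and 6-month BP with its interval, and carry that uncertainty into the confirmatory-trial simulations.

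The cost is a few extra fields in a chart abstraction that is already planned and one degree of freedom per model, about 1% of effective sample size if the covariate proves uninformative. No new patient procedure is needed.
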